8.0 CLINICAL TRIAL MATERIAL MANAGEMENT

This section contains information regarding the trial vaccine (HIL-214) and materials provided directly by the sponsor, and/or sourced by other means, that are required by the trial protocol, including important sections describing the management of clinical trial materials (CTM).

8.1 Trial Vaccine

HIL-214 for injection is provided by HilleVax, Inc. in single dose 1 mL pre-filled syringes as a 0.65 mL volume (to deliver a 0.5 mL dose). HIL-214 contains 50 µg GI.1/150 µg GII.4c VLPs and 500 µg of aluminum as Al(OH)₃.

HIL-214 does not contain a preservative.

The syringe contents may appear biphasic with a clear upper layer and a white precipitate. After mixing by shaking, a uniformly turbid suspension should be observed.

Each HIL-214 pre-filled syringe will be supplied in a tamper-evident, single dose carton.

8.2 Labeling

A clinical label will be affixed to trial vaccine containers in accordance with local regulatory requirements. Trial vaccine identity (label text) will state “HIL-214”) will be included on the trial vaccine container label.

8.3 Inventory and Storage

Vaccines will be shipped in refrigerated, temperature-controlled containers with a temperature monitor. The trial vaccine must be stored, kept away from light, and maintained at a controlled temperature of 2°C to 8°C (36°F to 46°F), as specified on the label. The trial vaccine must be kept in an appropriate, limited access, secure place until it is used or returned to the sponsor or designee for destruction. The trial vaccine must not be frozen. Each kit is intended for single use only.

Receipt and dispensing of trial vaccine must be recorded by authorized personnel at the trial site. All sponsor-supplied trial vaccine doses must be stored under the conditions specified on the label and remain in the original container until dispensed. A daily temperature log of the vaccine storage area must be maintained. Temperature excursions must be reported to the sponsor as soon as possible and use of these vaccines requires sponsor approval. Temperature excursion information can be found in the pharmacy manual.

8.4 Dose and Regimen

The trial vaccine 50 µg GI.1/ 150 µg GII.4c VLPs and 500 µg of aluminum as Al(OH)₃ will be administered intramuscularly as a single dose on Day 1 in the deltoid muscle, preferably of the non-dominant arm.

CONFIDENTIAL

8.5 Trial Vaccine Assignment and Dispensing Procedures

The investigator or designee will be responsible for overseeing the administration of the trial vaccine to subjects enrolled in the trial according to the procedures stipulated in this trial protocol.

Expired trial vaccines must not be administered.

8.5.1 Precautions to Be Observed When Administering the Trial Vaccine

Prior to trial vaccine administration, a subject must be determined to be eligible to receive trial vaccine (Sections 7.1 and 7.2), and it must be clinically appropriate in the judgment of the investigator.

Prior to trial vaccine administration, site staff must determine if the subject is eligible to receive the trial vaccine by evaluating the criteria listed in Sections 7.3 and 7.4.

Standard vaccination practices are to be observed and care should be taken when administering a trial vaccine intramuscularly in the deltoid muscle. In addition, World Health Organization (WHO) recommendations to reduce anxiety and pain at the time of vaccination should be followed [24]. Before administration of the trial vaccine, the injection site must be disinfected with a skin disinfectant (e.g., 70% alcohol). Allow the skin to dry. Refer to the pharmacy manual for details on preparation and administration of trial vaccine.

As with all injectable vaccines, trained medical personnel and appropriate medical treatment should be readily available in case of anaphylactic reactions following trial vaccine administration. For example, epinephrine 1:1000, diphenhydramine, and/or other medications for treating anaphylaxis should be available.

8.6 Randomization Code Creation and Storage

Not applicable.

8.7 Trial Vaccine Blind Maintenance

This is an open-label trial.

8.8 Unblinding Procedure

This is an open-label trial.

8.9 Accountability and Destruction of Sponsor-Supplied Clinical Trial Materials

The investigator or designee must ensure that the sponsor-supplied trial vaccine is used in accordance with the approved protocol and administered only to subjects enrolled in the trial. To document appropriate use of sponsor-supplied trial vaccine, the investigator must maintain records of all sponsor-supplied trial vaccine dose delivery to the site, site inventory, administration and use by each subject, and return to the sponsor or designee.

CONFIDENTIAL

Upon receipt of sponsor-supplied trial vaccine, the investigator or designee must verify the contents of the shipments against the packing list. The verifier should ensure that the quantity is correct, the trial vaccine is received within the labeled storage conditions (i.e., no cold chain break has occurred during transit), and is in good condition. If quantity and conditions are acceptable, investigator or designee will acknowledge receipt of the shipment.

If there are any discrepancies between the packing list versus the actual product received, the sponsor or designee must be contacted to resolve the issue. The packing list should be filed in the pharmacy investigator site file.

The investigator must maintain 100% accountability for all sponsor-supplied trial vaccine doses, and other CTM (including ancillary materials, as applicable) received and administered during their entire participation in the trial. Accountability includes, but is not limited to:

- Verifying that actual inventory matches documented inventory.
- Verifying that the log is completed for the vaccine lot (or trial vaccine ID or job number) used to prepare the trial vaccine.
- Verifying that all kits used are documented accurately on the log.
- Verifying that required fields are completed accurately and legibly.

If any dispensing errors or discrepancies are discovered, the sponsor must be notified immediately.

The investigator must record the current inventory of all sponsor-supplied trial vaccine doses on a sponsor-approved accountability log. The following information will be recorded at a minimum: protocol number and title, name of investigator, site identifier and number, description of sponsor-supplied trial vaccine, date, and amount. The log should include all required information as a separate entry for each subject to whom sponsor-supplied trial vaccine is administered.

The investigator will be notified of any expiry date or retest date extension of trial vaccine during the trial conduct. On expiry date notification from the sponsor or designee, the site staff must complete all instructions outlined in the notification, including segregation of expired CTM for return to the sponsor or designee for destruction.

All CTM will be provided by the trial site, sponsor or designee, depending upon availability. The list of CTM and source information can be found in the pharmacy manual. Prior to site closure or at appropriate intervals throughout the trial, before any CTM are returned to the sponsor or designee for destruction, a representative from the sponsor will perform CTM accountability and reconciliation. The investigator will retain a copy of the documentation regarding CTM accountability, return, and/or destruction, and originals will be sent to the sponsor or designee.

9.0 TRIAL PLAN

9.1 Trial Procedures

The following sections describe the trial procedures and data to be collected. For each procedure, subjects are to be assessed by the same investigator or site personnel whenever possible. The schedule of trial procedures is located in Section 2.2. All procedures must be performed by qualified and trained staff. Details about the trial procedures can be found in the procedures manual. All information collected should be recorded in the subject's electronic case report forms (eCRFs).

9.1.1 Informed Consent

The requirements of the informed consent form (ICF) are described in Section 15.2.

Informed consent must be obtained before any protocol directed procedures are performed.

A unique subject number will be assigned to each subject after informed consent is obtained. If all eligibility criteria are fulfilled (Sections 7.1 and 7.2), this subject number will be used throughout the trial. Subject numbers assigned to subjects who fail screening should not be reused (Section 9.1.11).

9.1.2 Demographics, Medical History, Prior Medications and Other Vaccinations

Demographic information to be obtained will include age/date of birth (if applicable), sex, race (and ethnicity) as described by the subject.

Medical history will also be collected, including but not limited to any medical history that may be relevant to subject eligibility for trial participation such as prior vaccinations, concomitant medications, and previous and ongoing illnesses and/or injuries. Relevant medical history can also include any medical history that contributes to the understanding of an AE that occurs during trial participation if it represents an exacerbation of an underlying disease/preexisting problem.

Medical history (including corresponding medication) to be obtained will include any significant conditions or diseases that have disappeared or resolved at or prior to signing of the ICF.

Adverse medical occurrences emerging during the time between signing of the ICF and administration of trial vaccine will be recorded in the medical history eCRF page. If such an adverse medical occurrence is assessed as related to a screening procedure this should be recorded as an AE related to trial procedure in the eCRF.

Details of all medications, vaccines and blood products administered or received by the subjects in the following timeframes will be collected as *prior* (prior to Day 1), or *concomitant* (from Day 1 to the end of the trial):

- Medications: from 2 months prior to Day 1 (day of trial vaccine administration), to the end of the trial.
- Vaccines: within 14 days before or after trial vaccine administration, to the end of the trial.
- Blood products: 90 days prior to Day 1 (day of trial vaccine administration), to the end of the trial.
- Antipyretics and/or analgesic medications within 24 hours prior to trial vaccine administration and the reason for their use (prophylaxis versus treatment) must be documented. Administration of the trial vaccine should be delayed if the subject has received antipyretics within 24 hours prior to trial vaccine administration.

Medications taken for prophylaxis are those intended to prevent the onset of AEs after trial vaccine administration. Medications taken for treatment are intended to reduce or eliminate the presence of symptoms that are present.

These data must be recorded in the source documents.

9.1.3 Documentation of Trial Entry

Only subjects for whom there is a signed ICF, who meet all of the inclusion criteria (Section 7.1) and none of the exclusion criteria (Section 7.2) are eligible for entry into the trial. Trial entry will be recorded in the subject screening and enrolment log.

9.1.4 Physical Examination

Physical examinations must be performed by a qualified health professional in accordance with local regulations and as listed within the site responsibility delegation log. A physical examination includes but is not limited to the following: a check of general appearance, auscultation of heart and lungs, palpation of the abdomen, and inspection of extremities (including skin over the intended injection site). A complete physical exam will be performed on Day 1, prior to trial vaccine administration, according to the investigator's standard practice. Additional symptom-directed physical examinations may be performed on Day 8 and Day 29 if indicated by review of the subject's medical history or if deemed necessary.

9.1.5 Vital Signs

During the physical examination, a subject should have their vital signs measured. These will include (but are not limited to), heart rate and body temperature. The investigator will follow standard of care for trial population and operational feasibility.

9.1.6 Immunogenicity Assessments

The immunogenicity assessments will include:

- Blood for the primary endpoint (proficiency panel) will be collected from all 80 subjects at Day 1 and Day 29, corresponding to approximately 100 mL of serum from a total 200 mL of blood from an individual subject.
- [REDACTED]

The blood sampling volumes are shown in [Table 9.a](#).

Table 9.a Blood Sampling Volumes

Sample	Day 1	Day 8	Day 29	Total volume per Subject
Blood for serum* and **	100 mL	-	100 mL	200 mL blood
[REDACTED] **	10 mL	-	10 mL	20 mL blood
[REDACTED]	30 mL	30 mL	30 mL	90 mL blood (total 110 mL)
Total volume per blood draw	140 mL	30 mL	140 mL	310 mL blood

Abbreviations:

Notes: *serum-based assays include histoblood group antigen (HBGA)-blocking assay, pan-Ig enzyme-linked immunosorbent assay (ELISA)

All samples must be collected in accordance with acceptable laboratory procedures. The maximum volume of blood taken at any single site visit is approximately 140 mL, and the approximate total volume of blood for the trial is maximum 310 mL.

9.1.7 Processing, Labeling and Storage of Biological Samples

All biological samples (e.g., blood and serum) will be processed, labeled, and stored according to the laboratory manual or other appropriate guideline provided to the site (Section [9.4](#)).

9.1.8 Safety Assessments

Safety assessments will include:

- For 7 days after vaccination (including the day of vaccination), solicited local AEs (injection site: pain, erythema, induration and swelling); solicited systemic AEs (headache, fatigue, myalgia, arthralgia, vomiting, and diarrhea), and body temperature.
- For 28 days after vaccination (including the day of vaccination), unsolicited AEs.
- Throughout the trial, SAEs and AEs leading to withdrawal from the trial.

Refer to Section [10.1](#) for safety definitions. Details on collection and reporting of AEs are in Section [10.5](#).

9.1.9 Contraception and Pregnancy Avoidance Procedure

For female subjects of childbearing potential, pregnancy testing (urine) will be performed on Day 1 prior to trial vaccine administration. All subjects will be provided with information on acceptable methods of contraception as part of the subject informed consent process and will be asked to sign a consent form stating that they understand the requirements for avoidance of pregnancy and donation of ova. In each case of delayed menstrual period (over one month between menstruations) confirmation of absence of pregnancy is strongly recommended.

Refer to Section 7.2.

9.1.10 Pregnancy

To ensure subject safety and the safety of the unborn child, each pregnancy occurring during the trial in a subject having received the trial vaccine must be reported to the sponsor promptly. If the subject agrees, the pregnancy must be followed to determine outcome, including spontaneous or voluntary termination, details of birth, and the presence or absence of any birth defects, congenital abnormalities, or maternal and/or newborn complications. If the subject agrees, this follow-up should occur even if the intended duration of safety follow-up for the trial has ended.

Any pregnancy occurring following trial vaccine administration should be reported immediately, using the paper pregnancy report form, to the contact listed in the investigator site file.

Should the pregnancy occur after administration of the trial vaccine, the investigator must inform the subject of their right to receive information concerning the trial vaccine.

Any SAE occurred during pregnancy should be reported throughout the trial as per timelines and procedures described in Section 10.4.

9.1.11 Documentation of Subjects Who Are Not Randomized

This trial is open-label.

Subject numbers assigned to subjects who fail screening should not be re-used.

9.2 Monitoring Subject Compliance

The investigator will record the injection of trial vaccine given to the subject.

9.3 Schedule of Observations and Procedures

The schedule for all trial-related procedures for all evaluations is shown in Section 2.2. Assessments should be completed at the designated site visit(s)/time point(s).

9.3.1 Pre-Vaccination Procedures (Day 1)

The following procedures must be performed before trial vaccine administration:

1. Informed consent (ICF) (Section 9.1.1).

CONFIDENTIAL

2. Assessment of eligibility criteria (Section 7.1 and Section 7.2).
3. Demographics (Section 9.1.2).
4. Medical history (Section 9.1.2).
5. Medication/vaccination history (Section 9.1.2).
6. Concomitant medications and vaccines (Section 9.1.2).
7. Documentation of trial entrance (Section 9.1.3).
8. Complete physical examination (Section 9.1.4).
9. Vital signs (Section 9.1.5).
10. Blood sampling (~ 140 mL) (Section 9.1.6).
11. Pregnancy test (Section 9.1.10).

9.3.2 Vaccination Procedures (Day 1)

After completing all pre-vaccination procedures (Section 9.3.1) and assessing the criteria for the delay of trial vaccine administration, the investigator will administer the trial vaccine according to the procedures described in Section 8.5.

9.3.3 Post-Vaccination Procedures (Day 1)

The following post-vaccination procedures will be performed on Day 1:

- Training of the subject on how to measure solicited local AEs and body temperature, how to complete the diary card and how often to complete the diary card. Training should be directed at the individual(s) who will perform the measurements of solicited local AEs and those who will enter the information into the diary card. This individual may or may not be the subject, but if a person other than the subject enters information into the diary card, this person's identity must be documented in the source and this person must receive training on the diary card. Training of the subject on how to measure an injection site AE and how to take their temperature, as well as how to record the information in the diary card, should be performed while the subject is under observation after vaccination.

Diary card instructions must include the following:

The individual(s) who will enter the information in the must understand that timely completion of the diary card on a daily basis is a critical component of trial participation.

Please note:

The diary card will be the only source document allowed for remote collection of solicited local and systemic AEs (including body temperature measurements). The following additional rules apply to the documentation of safety information collected by diary card:

- The diary card should be reviewed with the subject.
- No corrections or additions to the diary card will be allowed after it is reviewed with the investigator/designee.
- Any data that are identified as implausible or incorrect, and confirmed by the subject to be an error should be corrected by the subject on the diary card.
- Any blank fields on the diary card not otherwise corrected as above will be missing in the eCRF.

The site must enter all readable entries on the diary card into the eCRF.

- Any newly-described solicited safety information should be added to the diary card by the subject. Any new unsolicited safety information would be recorded in the subject's source document as a verbally-reported event and therefore captured as an AE and recorded in the AE eCRF.
- Starting on the day of trial vaccine administration, the subject will check for specific types of events at the injection site, any specific generalized symptoms (solicited systemic AEs), body temperature (any method), any other symptoms or change in the subject's health status, and any medications taken (excluding vitamins and minerals). These solicited AEs, body temperature, other symptoms and medications will be recorded in the diary card. Assessments should preferably take place in the evening.
- Temperature measurement is to be performed using the thermometer provided by the site. If the subject feels unusually hot or cold during the day, the subject should check their temperature. If the subject has fever, the highest body temperature observed that day should be recorded in the diary card.
- The measurements of solicited local AEs are to be performed using the ruler provided by the site.
- The collection in the diary card of body temperature, solicited local AEs, and solicited systemic AEs will continue for a total of 7 days after trial vaccine administration (Day 1).
- The use of analgesic/antipyretic medications to treat symptoms associated with trial vaccine administration will be recorded in the diary card during the reporting period (Day 1 to Day 7).

After trial vaccine administration, the subject will be observed for at least 30 minutes including observation for unsolicited AEs, solicited local AEs, solicited systemic AEs, and body temperature measurement. Information should be recorded in the eCRF. The investigator or delegate will take the opportunity to remind the subject how to measure solicited local AEs and body temperature as part of this observation period. All safety data will be collected in the subject's source documents.

The site staff should schedule the next trial activity reminder call or site visit.

CONFIDENTIAL

The subject will receive a written reminder of the next planned trial activity. The subject will be reminded to complete the diary card daily and to contact the site if there are any questions and to contact the site immediately (or as soon as the subject is medically stable) if the subject has a medical condition that leads to a hospitalization or an emergency room visit. All contact details will be provided to the subject.

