6.0 TRIAL DESIGN AND DESCRIPTION

6.1 Trial Design

This is a phase 2, single-arm, open-label trial for serologic assay validation, proficiency testing, safety and immunogenicity of HIL-214, in healthy adults aged 18 to 49 years. Vaccination with a single dose of HIL-214 will occur on Day 1.

[figure not shown]
There are 3 protocol-scheduled site visits (Day 1, Day 8, and Day 29) and 1 telephone contact (Day 85). Visits 1, 2, and 3 involve blood draws.

The final contact to collect safety data is scheduled on Day 85.

The trial design diagram is shown in Section 2.1. The schedule of procedures is shown in Section 2.2.

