10.2.2 Outcome of Adverse Events

The outcome of AEs can be described as follows:

Resolved: The subject has fully recovered from the event or the condition has returned to the level observed at baseline.

Resolving: The event is improving but the subject is still not fully recovered.

Not resolved: The event is ongoing at the time of reporting and the subject has still not recovered.

Resolved with sequelae: As a result of the AE, the subject suffered persistent and significant disability/incapacity (e.g., became blind, deaf or paralysed).

Fatal: The subject died due to the event. If the subject died due to other circumstances than the event, the outcome of the event per se should be stated otherwise (e.g., not resolved or resolving).

Unknown: If outcome is not known or not reported.

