13.1.4 Secondary Analysis - Safety

Safety data will be summarized by computing number and percentage of subjects who experienced an AE.

Solicited AEs

Solicited AEs will be assessed 30 minutes after administration of trial vaccine then daily for 7 days (including the day of administration). Summaries will be provided for each solicited AE, daily from Day 1 to Day 7 after administration of trial vaccine (including the day of dose) and overall. Solicited local AEs and systemic AEs will also be summarized by severity. For subjects

CONFIDENTIAL

with more than 1 episode of the same event within the Day 1 to Day 7 period, the maximum severity will be used for overall tabulations. Body temperature measurements will be summarized in categories (including fever, defined as temperature $\geq 38^{\circ}\text{C}$). Summaries of the day of first onset of each event and the number of days subjects experienced each event will also be provided. Data from the 30-minutes assessment will be summarized separately.

Unsolicited AEs

Unsolicited AEs, SAEs, and AEs leading to withdrawal from the trial will be coded using the MedDRA and summarized by preferred term (PT) and system organ class (SOC). Subjects reporting more than 1 occurrence for the term (level) being summarized will be counted only once for this term. Unsolicited AEs collected up to 28 days after administration (including the day of administration) of trial vaccine, will be summarized by severity (mild, moderate, severe) and relationship (not related, related) to trial vaccine or trial procedures. If a subject reported more than one AE within an SOC or PT then the event with the maximum severity and strongest relationship (causality) to trial vaccine or trial procedure will be included in the summaries. Any unsolicited AE will be summarized using the day of onset for the following 3 time intervals: 1) Day 1 to Day 28, 2) Day 1 to Day 7, and 3) Day 8 to Day 28.

SAEs and AEs leading to withdrawal from the trial will be summarized for Day 1 to Day 28, and overall (up to Day 85).

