13.3 Determination of Sample Size

A sample size of 80 subjects will provide sufficient serum for the establishment of proficiency panels to confirm assay validation of the validated serology assays planned to support the clinical development plan for HIL-214.

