### 5.3 Derived variables

#### 5.3.1 General

### **5.3.1.1 Baseline**

Unless otherwise stated, baseline is defined as the last non-missing pre-trial vaccine assessment prior to the administration of the trial vaccine.

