#### **10.1.3 Solicited Adverse Events**

The solicited safety parameters for this study are the local adverse events (injection site reactions) of pain, erythema (redness), induration and swelling and the systemic adverse events of headache, fatigue, myalgia, arthralgia, vomiting, diarrhea and fever (defined as body temperature greater than or equal to 38°C regardless of methods used).

Solicited reactions will be assessed 30 minutes after administration of the trial vaccine, and then daily for 7 days (including the day of administration).

Body temperature measurements will be summarized in categories (including fever), without adjustment for the route of measurement. Summaries of the day of first onset of each event and the maximum number of continuous days subjects experienced each event will also be provided.

Any solicited local or systemic reactions observed as continuing beyond 7 days following the trial vaccine dose will be recorded as an unsolicited AE in the case report form (CRF).

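### The six solicited systemic symptoms are not asked about or graded before the dose, so symptoms already present can be tabulated as Day 1 reactions, with no control arm to show the background rate

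*Protocol*

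**What the plan says.** **Before the dose.** Protocol 9.3.1 opens with "The following procedures must be performed before trial vaccine administration" and lists 11 items: consent, eligibility, demographics, medical history, medication and vaccination history, concomitant medications and vaccines, trial entry, physical examination, vital signs, a blood draw of about 140 mL, and a pregnancy test. No item covers the solicited systemic symptoms, and the schedule in Protocol 2.2 adds none.

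**After the dose.** Protocol 9.3.3 sets the first structured assessment: "the subject will be observed for at least 30 minutes including observation for unsolicited AEs, solicited local AEs, solicited systemic AEs". The diary starts the same day, and the site must transfer every legible diary entry to the eCRF. SAP 10.1.3 agrees on the timing: "Solicited reactions will be assessed 30 minutes after administration of the trial vaccine, and then daily for 7 days".

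**In the tables.** SAP 10.1.3.1 tabulates solicited reactions at 30 minutes, by day and over Days 1 to 7, with and without severity. It also summarizes day of first onset and duration. It gives no rule for a symptom that began before the injection and plans no solicited summary by relatedness. The restriction to events recorded after the dose, in SAP 10.1.4, applies to unsolicited AEs only.

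**Design.** Protocol 6.1: "This is a phase 2, single-arm, open-label trial for serologic assay validation, proficiency testing, safety and immunogenicity of HIL-214". Solicited systemic AEs are a named secondary endpoint (Protocol 5.2).

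**The concern.** Headache, tiredness and aches are common complaints that do not need a vaccine to explain them. In a controlled trial the comparator arm shows how often they occur anyway. Here there is no comparator, so the only way to see which symptoms were present at dosing is to ask at dosing, and the plan has no prompted question then.

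A subject who arrives with an untreated mild headache and still has it at the 30-minute check or at the evening diary entry can enter the 30-minute table, the Day 1 table and the Day 1 to 7 table. The first-onset summary would then show Day 1, and the duration would run from Day 1. What is at stake is the interpretation of the solicited systemic rates, onset days and durations.

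**Working it through.** **Step 1: is there any pre-dose capture, and does it reach the solicited tables?**

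| Pre-dose source | What it covers | Limit for the six symptoms |
|---|---|---|
| Vital signs (Protocol 9.1.5) | Temperature, heart rate | Covers fever, not the six symptoms |
| Physical examination (9.1.4) | General appearance, injection-site skin | Covers local signs; no symptom question |
| Medical history (9.1.2) | Ongoing illnesses; events between consent and dose | Unprompted, not graded by Table 10.b, kept on another form |
| Exclusion and delay rules (7.2, 7.3) | Active infection, temperature of 38.0°C or more, analgesic or antipyretic use in the prior 24 hours | An untreated headache, fatigue or ache meets none of these as such |
| Causality call (10.2) | Investigator judgement on solicited systemic AEs | SAP 10.1.3.1 plans no solicited table by relatedness |

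So partial capture exists, but none of it is a structured, graded check of the six symptoms, and none of it feeds SAP 10.1.3.1.

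**Step 2: is there a plan figure to reproduce?** No. The planned 80 subjects rest on serum supply ("A sample size of 80 subjects will provide sufficient serum for the establishment of proficiency panels to confirm assay validation"), and the documents give no expected symptom rate.

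**Step 3: possible size, for illustration.** Inputs:

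- n = 80 (Protocol 13.3).
- b = prevalence of a given symptom at dosing. Assumed 2 to 15%; not in the documents.
- r = true post-vaccination rate of that symptom. Assumed 10 to 30%; not in the documents.
- b and r are taken as independent, and every symptom present at dosing is taken to be recorded after the dose.

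Reported rate = 1 − (1 − r)(1 − b) = r + b(1 − r), so the rise is b(1 − r).

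| b | r = 10% | r = 20% | r = 30% |
|---|---|---|---|
| 2% | 11.8% (+1.8) | 21.6% (+1.6) | 31.4% (+1.4) |
| 5% | 14.5% (+4.5) | 24.0% (+4.0) | 33.5% (+3.5) |
| 10% | 19.0% (+9.0) | 28.0% (+8.0) | 37.0% (+7.0) |
| 15% | 23.5% (+13.5) | 32.0% (+12.0) | 40.5% (+10.5) |

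Smallest rise: 0.02 × 0.70 = 1.4 points. Largest: 0.15 × 0.90 = 13.5 points. In subjects, 80 × b(1 − r) runs from 80 × 0.014 = 1.1 to 80 × 0.135 = 10.8.

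**Step 4: would anyone be affected?** The chance that at least one of 80 has the symptom at dosing is 1 − (1 − b)^80, which is 80.1% at b = 2% and 98.3% at b = 5%.

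**Step 5: scale against sampling error.** With r = 20%, the exact 95% interval for 16/80 is 11.9 to 30.4%, a half-width of (30.4 − 11.9)/2 = 9.25 points. At b = 5% the expected count is about 19/80 (14.9 to 34.6%); at b = 10% it is 22/80 (18.1 to 38.6%). Over much of the assumed range the shift is therefore smaller than the sampling error. Unlike sampling error, it goes in one direction.

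**The case against.** The case against has real weight.

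- **Pre-dose capture exists.** A reader might infer that nothing is checked before the dose. That is not so: see Step 1. In particular, a headache brought on by the Day 1 draw arises between consent and injection, which Protocol 9.1.2 assigns to medical history, or to a procedure-related AE if judged so. This stands as a correction. The gap is the lack of a prompted, graded item linked to the solicited tables.
- **Miscounting is not instructed.** No passage says that a symptom present at dosing becomes a Day 1 reaction. Protocol 10.3 keeps intermittent events of pre-existing conditions out of the AE count, and the diary is reviewed with the subject. This stands: the miscount is inferred from missing rules. But the diary transfer rule and SAP 10.1.3.1 contain no filter that would prevent it.
- **Some recovery is possible.** A reader might conclude that the information is lost for good. SAP 8.4 codes and lists medical history, and solicited AEs are listed too, so recorded complaints can be cross-checked by subject. Recovery would be incomplete, because mild complaints may never be volunteered.
- **The baseline wording does not break.** A reader might think that outcomes cannot be assigned without a pre-dose grade, since Protocol 10.2.2 includes "the condition has returned to the level observed at baseline". Full recovery is the alternative in the same definition, so no grade is needed. SAP 5.3.1.1 ("baseline is defined as the last non-missing pre-trial vaccine assessment prior to the administration of the trial vaccine") is a general definition, and no planned solicited table uses change from baseline.
- **The size rests on assumptions.** The good-health, infection and analgesic rules probably lower prevalence at dosing. The range is for a common symptom and should not be carried over to vomiting or diarrhea.
- **Low stakes.** The endpoint is secondary and descriptive, and the bias would overstate reactogenicity. The procedures manual named in Protocol 9.1 is not available here and might contain such an item.

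These points limit the concern to a cheap improvement. They do not close the gap in the protocol and SAP.

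**Conclusion.** The concern holds in a limited form. Neither document provides a structured, graded pre-dose check of the six solicited systemic symptoms, so following the plan can report symptoms present at dosing as post-vaccination reactions with Day 1 onset. With one arm, the background rate cannot be shown any other way.

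The size is unknown. The range of about 1.4 to 13.5 points depends on the assumed prevalence, the assumed true rates, independence, and every such symptom being recorded after the dose. If symptomatic subjects are also more likely to react, or if their symptoms clear or go unrecorded, the rise is smaller. The effect is confined to a secondary safety endpoint.

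**What to change.** **Protocol 9.3.1 and the schedule in 2.2.** Add one step after the blood draw and before the injection: record presence and Table 10.b grade of headache, fatigue, myalgia, arthralgia, vomiting and diarrhea. State the look-back period on the form, because Table 10.b counts vomiting and diarrhea per 24 hours. The item is for analysis only and changes no eligibility or delay rule.

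**SAP 10.1.3.1.** Keep the planned counts and the planned onset summary. Add a row for symptoms that are new or of higher grade than before the dose, and a supplementary onset summary for those symptoms.

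**Cost.** One short eCRF item per subject at a visit that already takes place, plus one table row and one onset summary. Because the planned counts stay, comparability with other HIL-214 trials is kept.

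**Limit.** This separates only symptoms present at dosing. Background symptoms that arise later in Days 1 to 7 would still be counted, and without a control arm that remains a limitation to state in the report. For any subject dosed without the item, a listing that sets medical history beside solicited AEs would be a partial substitute.
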